6.2.2.3. Study Visit Week 12 (Day 85 ± 3 days)

The following tests and evaluations will be performed at the Week 12 Study Visit:

- Previous and concomitant treatments recording
- AE recording
- Physical examination (including weight)
- Vital signs (blood pressure and heart rate)
- Gynecological examination
- TVUS of uterus and ovaries including: uterus dimensions, myoma dimensions, endometrium thickness and assessment of ovaries
- Blood samples for hematology, coagulation parameters, chemistry, lipids, hormones (E2, P4). The subject must be fasting for the lipid blood sample
- Contraception counseling (not applicable in case of tubal ligation)
- Urinary protein dipstick
- Urine pregnancy test
- Return of soiled sanitary protection (if relevant and not already returned)
- eDiary check for good completion
- Assess iron intake (if applicable)
- Pain NRS, PGI-I, UFS QoL and EQ-5D questionnaires will be completed in the diary at site

At this visit, the subjects will be given new kits for the next 14 weeks of treatment. The kit numbers will be provided by the IWRS. The subject will be reminded to take one tablet from each blister and one capsule daily.

6.2.2.4. Study Visit Week 24 (Day 169 ± 3 days)

The following tests and evaluations will be performed at the Week 24 Study Visit:

- Previous and concomitant treatments recording
- AE recording
- Physical examination (including weight)
- Vital signs (blood pressure and heart rate)
- Gynecological examination
- TVUS of uterus and ovaries including: uterus dimensions, myoma dimensions, endometrium thickness and assessment of ovaries

- Endometrium biopsy, unless the endometrium thickness in TVUS is ≤ 5 mm, in which case no endometrium biopsy will be necessary, as far as the screening biopsy has provided assessable results. Appropriate photo documentation of the endometrium thickness is mandatory and will be kept in the source documents. If the subject is menstruating at the time of the visit, the biopsy can be performed at another time
- Blood samples for hematology, coagulation parameters, chemistry, lipids, hormones (E2, P4). The subject must be fasting for the lipid blood sample
- Contraception counseling (not applicable in case of tubal ligation)
- Urinary protein dipstick
- Urine pregnancy test
- Return of soiled sanitary protection (if relevant and not already returned)
- eDiary check for good completion
- Assess iron intake (if applicable)
- Pain NRS, PGI-I, UFS QoL and EQ-5D questionnaires will be completed in the diary at site
- BMD assessed by DXA for femoral neck, hip and spine. DXA can be performed ±10 days from Week 24 visit

At this visit, the subjects will be given new kits for the next 14 weeks of treatment. The kit numbers will be provided by the IWRS. The subject will be reminded to take one tablet from each blister and one capsule daily.

6.2.2.5. Study Visit Week 28 ± 7 days and Week 32 ± 7 days

The following tests and evaluations will be performed at the Week 28 and Week 32 Study Visits:

- Previous and concomitant treatments recording
- AE recording
- Vital signs (blood pressure and heart rate)
- Blood samples for hematology and chemistry
- Contraception counseling (not applicable in case of tubal ligation)
- Urinary protein dipstick
- Urine pregnancy test
- Return of soiled sanitary protection (if relevant and not already returned)
- eDiary check for good completion
- Assess iron intake (if applicable)

6.2.2.6. Study Visit Week 36 ± 7 days

The following tests and evaluations will be performed at the Week 36 Study Visit:

- Previous and concomitant treatments recording
- AE recording
- Physical examination (including weight)
- Vital signs (blood pressure and heart rate)
- Gynecological examination
- TVUS of uterus and ovaries including: uterus dimensions, myoma dimensions, endometrium thickness and assessment of ovaries
- Blood samples for hematology, coagulation parameters, chemistry, lipids, hormones (E2, P4). The subject must be fasting for the lipid blood sample
- Contraception counseling (not applicable in case of tubal ligation)
- Urinary protein dipstick
- Urine pregnancy test
- Return of soiled sanitary protection (if relevant and not already returned)
- eDiary check for good completion
- Assess iron intake (if applicable)
- Pain NRS, PGI-I, UFS QoL and EQ-5D questionnaires will be completed in the diary at site

At the Week 36 visit, the subjects will be given additional 14-week kits for the rest of the treatment period. The kit numbers will be provided by the IWRS. The subject will be reminded to take one tablet from each blister and one capsule daily and must be instructed to finish the kits she already has before starting the new kits so that she has enough up to the Week 52 visit.

6.2.2.7. Phone calls

Between the Week 36 and Week 52 visits, the site will call the subject monthly to check her wellbeing and remind her about study procedures (diary, alkaline hematin, medication intake, contraception). Prior to the call, the site will monitor the subject's electronic diary data.

6.2.2.8. Study Visit Week 52 – End of Treatment Visit

This visit must occur prior to last IMP intake (i.e. no longer than 28 weeks after the Week 24 visit). The following tests and evaluations will be performed at the Week 52 Study Visit:

- Previous and concomitant treatments recording
- AE recording

- Physical examination (including weight)
- Vital signs (blood pressure and heart rate)
- Gynecological examination, including manual breast examination (by palpation)
- PAP smear
- TVUS of uterus and ovaries including: uterus dimensions, myoma dimensions, endometrium thickness and assessment of ovaries
- Endometrium biopsy, unless the endometrium thickness in TVUS is ≤ 5 mm, in which case no endometrium biopsy will be necessary, as far as the screening or week 24 biopsy has provided assessable results. Appropriate photo documentation of the endometrium thickness is mandatory and will be kept in the source documents. If the subject is menstruating at the time of the visit, the biopsy can be performed at another time
- Blood samples for hematology, coagulation parameters, chemistry, lipids, hormones (E2, P4). The subject must be fasting for the lipid blood sample
- Contraception counseling (not applicable in case of tubal ligation). Non-hormonal contraception should be continued up to 12 weeks after last day of treatment (Week 64), however contraception (hormonal or non-hormonal) must be maintained up to the end of the study (Week 76).
- Urinary protein dipstick
- Urine pregnancy test
- Return of soiled sanitary protection (if relevant and not already returned)
- eDiary check for good completion
- Assess iron intake (if applicable)
- Pain NRS, PGI-I, UFS QoL and EQ-5D questionnaires will be completed in the diary at site
- BMD assessed by DXA for femoral neck, hip and spine. DXA can be performed ± 10 days from Week 52 visit
- The subject will be verbally asked which treatment she believed she received during the blinded treatment period. The answer will be recorded in the eCRF

The subject will return all used and unused blisters and continue in the treatment-free follow-up period.

6.2.3. Follow-up period without treatment

Up to the Week 64 study visit, the subject will be asked to record her uterine bleeding pattern daily in her eDiary at approximately the same time each evening.

6.2.3.1. Study Visit Week 64 ± 7 days

The following tests and evaluations will be performed at the Week 64 Study Visit:

- Previous and concomitant treatments recording
- AE recording
- Physical examination (including weight)
- Vital signs (blood pressure and heart rate)
- Gynecological examination
- TVUS of uterus and ovaries including: uterus dimensions, myoma dimensions, endometrium thickness and assessment of ovaries
- Endometrium biopsy if the Week 52 biopsy was not assessable, not done or diagnosis was not benign. If no tissue is available, the biopsy should be repeated as soon as possible in the following days
- Blood samples for hematology, coagulation parameters, chemistry, lipids, hormones (E2, P4, FSH (if menstruations have not returned)). The subject must be fasting for the lipid blood sample
- Contraception counseling (not applicable in case of tubal ligation)
- Urinary protein dipstick
- Urine pregnancy test
- eDiary check for good completion
- Pain NRS, PGI-I, UFS QoL and EQ-5D questionnaires will be completed in the diary at site

6.2.3.2. Study Visit Week 76 \pm 7 days – End of Follow-up Visit

The following evaluation will be performed at Week 76 Study Visit:

- BMD assessed by DXA for femoral neck, hip and spine. DXA can be performed ± 10 days from study visit
- AE recording if related to BMD loss
- Previous and concomitant treatments recording only if treatments with potential impact on BMD
- Urine pregnancy test
- Completion of the eCRF exit form

6.2.4. Planned extension of the study

Not applicable.

6.3. EFFICACY OBSERVATIONS AND MEASUREMENTS

All endpoints relating to bleeding, including amenorrhea and time to amenorrhea will be based on the alkaline hematin data.

6.3.1. Menstrual blood loss

6.3.1.1. Menstrual blood loss volume - Alkaline hematin method

Menstrual bleeding encompasses any bleeding experienced during a menstrual cycle. Menstrual blood loss volume will be measured using the alkaline hematin method throughout the study up to Week 52. During this timeframe, all soiled sanitary protection will be collected and sent to a laboratory for analysis. For eligibility, menstrual blood loss during the first eight days of two screening menstrual periods must be > 80 mL. If menstrual blood loss during the first eight days of the first cycle is \leq 80mL due to missed collection of sanitary products, the subject can be retrained, menstrual blood loss at screening would then be evaluated on the next two menstrual cycles.

The return of soiled sanitary protection will be arranged between the site and the subject. Soiled sanitary protection must be shipped to the laboratory within no more than 3 weeks. The sanitary products must be received by the laboratory within 3 weeks of collection. The subject must be instructed to return the transportation box to the investigator's site either once it is full or after a collection period of a maximum of 12 days. During the second menstrual period (or third if applicable), the box should be returned by the subject after the first 8 days of collection. Containers with materials collected during the same day of bleeding should always be returned together and not split over two shipments.

6.3.1.2. Amenorrhea

Amenorrhea will be determined using the alkaline hematin method and is defined as having no sanitary material returned or volume < lower limit of quantification within at least a 35-day interval. Amenorrhea will be assessed using data up to Week 24, i.e. at least a 35-day interval up to Week 24 and again using all data up to Week 52.

6.3.1.3. Uterine bleeding scale

The subject will complete a daily questionnaire in the eDiary assessing the incidence and amount of uterine/vaginal bleeding in the last 24 hours. The primary purpose of this eDiary is to monitor the subject's compliance with shipping soiled sanitary products for the alkaline hematin method. The incidence and strength of uterine bleeding will be assessed using the following scale:

Please select the heaviest vaginal bleeding level you experienced over the last 24 hours			
None	No bleeding nor spotting		
Spotting	Blood loss not requiring sanitary protection (except for panty liners)		
Bleeding	Blood loss requiring sanitary protection (tampons or pads)		
Heavy Bleeding	 Heavy blood loss requiring sanitary protection (tampons or pads) for example: Need for double protection to manage menstrual bleeding Menstrual bleeding accompanied by sensation of "gushing" or "flooding" Soaking one pad and/or tampon or more per hour for three or more consecutive hours Needing to change the tampon or pad at night or soiling bedclothes 		

6.3.2. Quality of life

6.3.2.1. Uterine Fibroid symptom severity and health-related quality of life

Symptom severity and quality of life will be assessed by the subject at Day 1, Week 12, Week 24, Week 36, Week 52 and Week 64 visits.

Subjects will complete the UFS-QoL questionnaire (APPENDIX B) at site in the eDiary. At the appropriate visits, the site staff will set up the device so that the questionnaire appears.

6.3.2.2. EQ-5D

Subjects will complete the EQ-5D-5L questionnaire (APPENDIX C) at Day 1, Week 12, Week 24, Week 36, Week 52 and Week 64 visits. Subjects will complete the questionnaire at site in the eDiary. At the appropriate visits, the site staff will set up the device so the questionnaire appears.

6.3.3. Pain NRS

Subjects will record pain on a Numeric Rating Scale (NRS) (APPENDIX D) at Day 1, Week 12, Week 24, Week 36, Week 52 and Week 64 visits. Subjects will complete the questionnaire at site in the eDiary. At the appropriate visits, the site staff will set up the device so the questionnaire appears.

6.3.4. Patient Global Impression of Improvement (PGI-I)

The Patient Global Impression of Improvement questionnaire (APPENDIX E) will be completed at Week 12, Week 24, Week 36, Week 52 and Week 64 visits. Subjects will complete the questionnaire at

site in the eDiary. At the appropriate visits, the site staff will set up the device so the questionnaire appears.

6.3.5. Myoma and uterus volume

Total volume of the three largest myomas and uterus volume will be measured using transvaginal ultrasound at Screening and at Week 12, Week 24, Week 36, Week 52 and Week 64. If transvaginal ultrasound is not possible, abdominal ultrasound can be used.

For the myomas, the operator should measure the three dimensions of each of the largest three myomas visible at the visit, even if these are not the ones that were previously measured. For correct volume assessment, the operator will be requested to record the myomas in three dimensions and to photodocument the measurements in the source data.

For the uterus volume, the operator should measure in three dimensions the length (from Cervix to outer fundus) and width and thickness and photodocument each measurement.

If possible, the transvaginal ultrasound should be performed by the same operator at each visit.

6.4. SAFETY OBSERVATIONS AND MEASUREMENTS

6.4.1. Adverse Events

An adverse event (AE) is defined as any untoward medical occurrence in a clinical trial subject administered an investigational medicinal product (IMP) and which does not necessarily have a causal relationship with this treatment. It can therefore be any unfavorable sign (including an abnormal laboratory finding), symptom or disease temporally associated with the use of an IMP, whether or not considered related to the IMP.

For screening failure subjects, adverse events and updates must be recorded in the eCRFs using the AE or SAE forms (as appropriate) until the date the subject is determined to be a screening failure. Beyond that date, only serious or medically relevant events will be followed up.

6.4.2. Vital signs

Blood pressure (BP) and heart rate will be measured in sitting position at Screening and from Day 1 at each visit up to the Week 64 visit. In case of abnormal vital signs (i.e. $BP \ge 150/100 \text{ mmHg}$ or $\le 90/50 \text{ mmHg}$ and/or heart rate $\ge 100 \text{ bpm}$ or $\le 40 \text{ bpm}$) and if the abnormality is not pre-existing, a repeat assessment after 5 min should be taken. In case of confirmed abnormality, an AE must systematically be reported by the Investigator in the eCRF AE page. The Investigator is to provide a diagnosis rather than reporting of individual vital signs parameters whenever possible.

6.4.3. Physical examination

A complete physical examination, i.e. weight, examination of organ systems, including thyroid gland, lungs, heart, abdomen, liver, kidneys and peripheral pulses (by palpation, auscultation or percussion), eyes, ears, nose, throat and skin (by inspection) and neurological reflexes will be performed at Screening, on Day 1 and at the Week 12, 24, 36, 52 and 64 visits.

A gynecological exam will be performed at Screening, Week 12, 24, 36, 52 and 64 visits. In addition, a manual breast examination (by palpation) will be performed at Screening and Week 52 visits. Results of the examinations will be recorded on in the source subject data file and in the eCRF.

6.4.4. Transvaginal ultrasound and endometrial biopsies

In addition to the efficacy assessments (myoma and uterus volume) a number of safety measurements will be made during the TVUS. At the Screening, Week 12, 24, 36, 52 and 64 visits, the operator will measure endometrium thickness, assess ovaries and report any abnormality (adenomyosis, polyp, etc). The print-outs of the ultrasound will be interpreted and commented and kept as source data. Results of the examination will be recorded on source data forms and in the eCRF. If transvaginal ultrasound is not possible, abdominal ultrasound can be used.

Endometrial biopsies will be performed for histological assessment during Screening, at Weeks 24 and 52. At Week 64, an endometrial biopsy will only be taken if no endometrial biopsy was obtained at Week 52 or diagnosis at Week 52 was different from "benign endometrium". For subjects who demonstrate significant bleeding irregularities that differ from their typical pattern or the expected pattern due to study drug, unscheduled biopsies are to be taken. Endometrial biopsy samples will be collected with the Pipelle de Cornier® or equivalent (APPENDIX F), as will be described in the manual provided by the central laboratory. Endometrial biopsies will be centrally assessed by pathologists in the selected central laboratory blinded to treatment group.

The endometrium biopsy is not required at the Screening visit for subjects having performed an endometrium biopsy within the past 6 months of the Screening visit, which shows no endometrium atypical hyperplasia or adenocarcinoma and for which report is available in source documents and slides are available to be provided if requested for current study assessment through retrospective central laboratory reading.

If the result of the endometrium biopsy is not yet available at the time of randomization, the subject can be randomized. If there is a subsequent clinically significant finding in the biopsy, the subject will be withdrawn immediately.

In case of multiple (at least two) and unsuccessful attempts to get sufficient endometrial tissue, the subject is allowed to be randomized without any screening endometrial biopsy under the following conditions:

a) The investigator confirms and documents in source that the subject has no signs of suspected endometrium malignancy (e.g. abnormal bleeding profile)

b) The investigator and subject agree that at end of treatment all necessary actions will be taken to get a sufficient endometrium sample (e.g. short anaesthesia, if necessary)

c) The medical monitor of the study approves the randomization of the subject.

If biopsy samples collected during the study are inadequate and cannot be analysed by the laboratory they must be repeated as follows:

- Week 24 biopsy must be repeated at Week 36
- Week 52 biopsy must be repeated as soon as possible

- Week 64 biopsy must be repeated as soon as possible

In case of endometrial hyperplasia without atypia, the biopsies taken at Weeks 24, 52 and 64 must be repeated. In case of endometrial hyperplasia with atypia or in case of neoplasma, the laboratory will send an alert and the medical monitor will contact the sites to discuss the proceeding in line with local practice.

In case of dilatation and curettage during the study, which will be by definition a SAE, pathology results will be requested as part of the SAE follow-up information.

6.4.5. Bone mineral density and DXA

Bone mineral density (BMD) of femoral neck, hip and spine will be assessed by DXA at Day 1 and Weeks 24, 52 and 76.

All DXA scans will be read by a central imaging laboratory. Each site will use the same machine for the duration of the study under the supervision of a nominated primary technologist at the site. There will also be centralized monitoring of DXA scan quality for each site including a pre-qualification phantom scan, cross-calibration phantom scan and a monthly review of daily QC data.

In the event a scan does not meet quality standards a repeat scan request will be sent to the site. There will be predefined stopping rules for subjects.

Subjects presenting with a Z-score \leq -2 assessed on the DXA at Day 1 will have to discontinue study treatment.

If there is more than 5% BMD loss on any one parameter a repeat DXA scan will be requested. If the Week 24 repeat scan shows more than 8% loss on any one parameter (femoral neck, hip or spine) or a Z-score \leq -2.5, the subject will be required to stop treatment.

Detailed information on the centralized reading and QC and the stopping rules will be included in the Imaging Acquisition Guidelines and Imaging Reference Manual.

6.4.6. Laboratory parameters

- Serum levels of TSH will be assessed at Screening.
- Serum levels of FSH will be assessed at Screening and at Week 64 if menstruations have not returned.
- Serum levels of E2 and progesterone [P4] will be assessed from blood samples taken at Day 1 and Weeks 4, 8, 12, 24, 36, 52 and 64. These results will not be communicated to the site or study team.
- Hematology and chemistry (see APPENDIX G) will be assessed from blood samples taken at Screening, Day 1 and Weeks 4, 8, 12, 24, 28, 32, 36, 52 and 64.
- Fasting lipids will be assessed from blood samples taken at Day 1 and Weeks 12, 24, 36, 52 and 64.

• Coagulation parameters (see APPENDIX G) will be assessed from blood samples taken at Screening, Day 1 and Weeks 12, 24, 36, 52 and 64.

Blood samples will be analyzed by the central laboratory. Details of blood sampling process, sample handling and shipment are described separately in a laboratory manual provided by the central laboratory. Central laboratory reference ranges will be filed in the investigator site file and in the trial master file.

The laboratory parameters are listed in APPENDIX G.

6.5. CONCOMITANT MEDICATIONS AND THERAPIES

The Investigator will record in the appropriate section of the eCRF all concomitant medications taken by the subject during the study, from 30 days prior to the date of signature of informed consent and for the duration of the reporting period as defined in section 8.5. From Week 64 onwards, only concomitant medication with potential impact on BMD will be recorded in the eCRF.

6.5.1. Permitted Medicines

Any medications other than those excluded by the protocol (see section 5.2.2 or 6.5.2), which are considered necessary for the subject's welfare and/or which will not interfere with the study medication, may be given at the discretion of the Investigator.

Contraceptive use:

For subjects of childbearing potential and requiring contraception, non-hormonal contraception is required from the beginning of the screening period until 12 weeks after the end of treatment. Two forms of non-hormonal contraception will be required, e.g. condom with spermicide. Suitable condoms with spermicide (or condoms and spermicide separately) will be provided free of charge to subjects over the duration of the study.

Hormonal contraception including hormonal IUD must be stopped following ICF signature until 12 weeks after end of treatment. A washout period of 1 month must be allowed prior to screening assessments.

Between Week 64 and Week 76, the subject must continue to use contraception, however hormonal and non-hormonal methods are acceptable.

Iron supplementation:

Iron supplementation will be provided to the sites.

If at any visit (including screening) the subject's hemoglobin levels are below 10 g/dL (but higher than 6 g/dL at screening), iron supplementation should be given until the subject's hemoglobin levels increase by at least 2 g/dL and are above the lower limit of central lab normal range (12 g/dL). Once normal levels are reached, iron supplementation is to be stopped.

Iron supplements are reported to decrease absorption of concomitantly administered drugs - in the absence of drug interaction data with OBE2109, iron supplements will be taken at least four hours apart from OBE2109 intake. It is recommended to take the study IMP in the morning and the iron

supplementation with the lunch or evening meal but at least 30 minutes before going to bed. The iron supplement tablets should be taken with a glass of water.

While under iron supplementation, the subject must bring the used and unused blisters to the site at every visit so that the iron intake can be assessed.

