The sanitary products must be received by the laboratory within 3 weeks of collection. The subject must be instructed to return the transportation box to the investigator's site either once it is full or after a collection period of a maximum of 12 days. During the second screening menstrual period (or third if the first period was ≤ 80 mL), the box should be returned by the subject after the first eight days of collection.

During screening, the site will receive the results of the Alkaline Hematin Method on a regular basis. If menstrual blood loss is ≤ 80 mL for the first eight days of the first menstrual period due to missed collection of sanitary protection, the subject can be offered the possibility to measure menstrual blood loss over two further cycles. The subject should be re-trained on the alkaline hematin method prior to starting the second cycle.

Subjects will be provided with iron supplements if Hemoglobin (Hb) levels are below 10 g/dL.

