9.5. DATA ANALYSIS

More details of the proposed statistical analysis will be documented in the Statistical Analysis Plan (SAP), which will be finalized prior to the database lock and unblinding of the Week 24 data.
Categorical data will be presented using counts and percentages of subjects, while continuous variables will be presented using the mean, standard deviation, median, 1st and 3rd quartiles, minimum, maximum, and number observations. Raw data will be listed.

Individual OBE2109 treatment group versus placebo comparisons will be made for superiority with an overall two-sided Type I error (alpha) of 0.05. In order to account for multiplicity given four different OBE2109 treatment groups, each primary endpoint comparison versus placebo will be conducted at the 0.0125 level of significance, i.e. 0.05 divided by 4. In addition, a sequential testing procedure within each OBE2109 treatment group will be used for the comparison of the following secondary endpoints versus placebo, where a formal statement of efficacy may be made, thus continuing to protect the overall type I error. An endpoint will only be claimed to be statistically significant if the resulting p-value for that endpoint and all endpoints higher up the testing order (for a given treatment arm) are less than 0.0125:

- 1. Reduced menstrual blood loss at 24 weeks of treatment (primary endpoint)
- 2. Time to reduced menstrual blood loss (i.e. \leq 80 mL and \geq 50% reduction from baseline) up to Week 24
- 3. Amenorrhea up to Week 24
- 4. Time to amenorrhea up to Week 24
- 5. Number of days of uterine bleeding for the 28-day interval up to Week 24
- 6. Hemoglobin level at Week 24

The additional efficacy endpoints will be tested at the 0.0125 with no further adjustments for multiplicity.

Unadjusted, ninety five percent (95%) confidence intervals will be presented throughout. Hypothesis testing (as described above) will be used to formally establish an effect, prior to returning to the estimation framework.

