In general, between group comparisons for continuous endpoints will be analyzed via repeated measures analysis of covariance, including the baseline and stratification factor race as a covariate, with each treatment group compared versus placebo using contrasts.

Mean hemoglobin will be compared between treatment groups and categorical analyses may also be performed.

Fibroid volume and uterine volume are expected to be log-normally distributed and so will be logtransformed prior to analysis, with the subsequent results (mean differences and corresponding confidence intervals) back transformed and hence reported in terms of ratios. The underlying distributions will be checked, and if deemed necessary alternative analyses may also be conducted. The number of days of uterine bleeding (assessed via the alkaline hematin method) will be analyzed using a negative binomial model or zero-inflated negative binomial, depending on model fit. The PGI-I will be analysed using Mantel-Haenszel methodology.

In order to explore the impact of submucosal fibroids on the efficacy of OBE2109, an analysis of the primary efficacy endpoint will be performed on the subset of patients from the FAS analysis set with a baseline FIGO classification of 0, 1 or 2 in either one fibroid only or in any fibroid, depending on the number of available fibroid data.

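### The hemoglobin model omits iron use before first dose, and the protocol does not say that the Week 24 comparison is made regardless of iron started later

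*Protocol*

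**What the plan says.** Section 2.1.2 of the protocol lists hemoglobin among the outcomes on which superiority over placebo is to be demonstrated. Section 9.5 places "Hemoglobin level at Week 24" sixth and last in the sequence run within each active arm. A claim requires that the p-values for the endpoint and "all endpoints higher up the testing order (for a given treatment arm) are less than 0.0125".

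Section 6.5.1 sets the start of iron: "If at any visit (including screening) the subject's hemoglobin levels are below 10 g/dL". It also sets the end: "iron supplementation should be given until the subject's hemoglobin levels increase by at least 2 g/dL and are above the lower limit of central lab". The same sentence puts that limit at 12 g/dL. Section 6.2.1 already applies the rule in screening: "Subjects will be provided with iron supplements if Hemoglobin (Hb) levels are below 10 g/dL". Section 6.4.6 says that hematology "will be assessed from blood samples taken at Screening, Day 1 and Weeks 4, 8, 12, 24, 28, 32, 36, 52 and 64".

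For the analysis, section 9.5.3 says "Mean hemoglobin will be compared between treatment groups and categorical analyses may also be performed". The general model for continuous endpoints is "repeated measures analysis of covariance, including the baseline and stratification factor race as a covariate". Neither section 9.5.3 nor section 9.5.5 (missing data) mentions iron. The only outcome rules tied to interventions are the non-responder rules for the binary primary endpoint in section 9.5.2.

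**The concern.** The variable under test also triggers a treatment meant to raise it. If the drug reduces bleeding, placebo women should fall below 10 g/dL more often after Day 1. They should also stay on iron longer, because the stop rule needs both a 2 g/dL rise and a value above 12 g/dL. Both effects lift the placebo mean at Week 24.

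There is a separate matter of precision. Screening lasts up to 17 weeks, and a woman may begin iron during it. Two women with the same Day 1 hemoglobin, one rising on iron and one not, are likely to follow different courses, and a model with only baseline hemoglobin and race cannot separate them.

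At stake are the hemoglobin claim itself and its meaning. The protocol does not say whether the claimed effect is that of the drug with iron given as needed in both arms, or that of the drug had no further iron been started.

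**Working it through.** **The plan's own figure.** The only powered figure is 64 per arm for the primary endpoint (section 9.2: 30% against 70%, two-sided 0.0125, at least 90% power for all four comparisons). It reproduces: 63 per arm with continuity correction at a pairwise power of 0.90^(1/4) = 0.974. At 64 per arm, Fisher's exact test has power 0.975 per pair, and 0.975^4 is about 0.90. No figure in the protocol concerns hemoglobin, so the inputs in steps 2 to 4 are assumptions, apart from 100 per arm (section 5.1.2) and 0.0125 (section 9.5).

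**Step 1. When iron can separate the arms.**
- Screening or Day 1 sample: the trigger precedes treatment, so randomization balances who starts. How long they stay on iron can still differ by arm.
- Weeks 4, 8 and 12: new starts can differ by arm. A Week 12 start has 12 weeks to act.
- Week 24: a start here cannot affect the Week 24 value.

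**Step 2. Simple attenuation formula.** Observed difference = true difference − (excess share of placebo women on iron) × (mean gain from iron by Week 24). Power at 100 per arm = Φ(difference/SE − 2.50), with SE = SD × √(2/100). For SD 1.5 the SE is 0.21 g/dL.

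| True difference (g/dL) | Excess on iron | Gain (g/dL) | Observed (g/dL) | Lost | Power, SD 1.5 |
|---|---|---|---|---|---|
| 1.0 | 10 points | 1 | 1.0 − 0.1 = 0.9 | 10% | 0.987 → 0.960 |
| 1.0 | 20 points | 2 | 1.0 − 0.4 = 0.6 | 40% | 0.987 → 0.630 |
| 1.0 | 30 points | 2 | 1.0 − 0.6 = 0.4 | 60% | 0.987 → 0.270 |
| 0.6 | 10 points | 1 | 0.6 − 0.1 = 0.5 | 17% | 0.630 → 0.444 |
| 0.6 | 30 points | 2 | 0.6 − 0.6 = 0.0 | 100% | 0.630 → 0.006 |

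With SD 1.2 and a true difference of 1.0 g/dL, power falls from 1.000 to between 0.997 and 0.444 over the same range of 10 to 30 points and 1 to 2 g/dL.

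**Step 3. Simulating the rule itself.** The formula takes the excess share as given. A simulation instead applied the start and stop rules from Day 1 to Week 24 and analysed the result by baseline-adjusted ANCOVA. Assumed inputs were a baseline mean of 10.5 to 11.5 g/dL with SD 1.4, a no-iron difference of 1.0 to 1.7 g/dL, and an iron gain of 0.15 to 0.5 g/dL per 4 weeks. The placebo excess on iron came out at only 5 to 12 points. Between 3% and 24% of the difference was lost, and power stayed at about 1.00.

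**Step 4. Value of the pre-dose covariate.** In a simulation of the iron rule under assumed inputs, adding iron use before first dose cut the variance of the treatment effect by about 2% to 18% without shifting the estimate. In sample-size terms, 100 per arm would work like 100/0.98 = 102 to 100/0.82 = 122 per arm.

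**The case against.** The strongest reply is that nothing here is wrong. One blinded iron rule applies in all arms. Comparing means regardless of iron estimates a valid treatment-policy effect: drug plus iron as needed against placebo plus iron as needed. It errs toward no difference and does not inflate type I error. Hemoglobin is last in the order, so a miss blocks no other claim. Section 9.5 defers detail to the SAP, and the model is introduced as applying in general. Most of this stands, and it is why the confirmatory comparison should remain regardless of iron. It does not remove the point. The protocol itself fixes the iron rule, the confirmatory rank and the covariates, and together they leave the meaning of the claim implicit and a useful pre-dose covariate unused.

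A reader might infer three stronger conclusions that the documents do not support.
- *Iron hides the drug's effect.* No iron-use rate, spread or response is given, and the simulated rule leaves most of the difference intact.
- *Iron raises hemoglobin by at least 2 g/dL.* The stop rule says when iron ends, not what it achieves. A woman who never gains 2 g/dL stays on iron, and in an active arm the gain may come from reduced bleeding.
- *Iron starters should be scored at their last pre-iron value, as the primary endpoint scores failures.* Those values are selected for being below 10 g/dL, so carrying them forward locks in regression to the mean. If placebo starts more iron, it tilts the estimate toward the drug. It also departs from section 9.5.5, which leaves missing continuous values to the likelihood model, and the non-responder rules in section 9.5.2 do not cover a permitted supplement.

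**Conclusion.** The point holds as one of precision and clarity. The stated hemoglobin model omits iron use before first dose, a pre-treatment variable likely to predict the later course. The protocol also does not say that the Week 24 effect is estimated regardless of iron started or prolonged after Day 1.

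If the drug reduces bleeding, the expected direction is attenuation toward zero. The size cannot be derived from the documents. For a true difference of 1.0 g/dL or more, the assumed inputs give a loss of about 3% to 60%, with the low end from applying the rule itself and the high end from the simple formula. For 0.6 g/dL with heavy differential iron use, the loss could be total. The precision gain of about 2% to 18% in variance also rests on assumed inputs. Only the hemoglobin claim is exposed.

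**What to change.** Leave the iron rule unchanged. In section 9.5.3, and in the SAP before the Week 24 unblinding:

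1. Add iron use before first dose on Day 1 (yes/no) as a covariate in the hemoglobin model. Section 6.2.2.1 already lists iron intake among the Day 1 assessments made before dosing.
2. State that the confirmatory Week 24 comparison is made regardless of iron started or continued after Day 1.
3. Pre-specify one supplementary analysis that treats iron started after Day 1 as an intercurrent event. Examples are a composite with iron start as failure, or a hypothetical no-iron estimate by multiple imputation. Say how iron prompted by the Day 1 sample is classified.
4. Report iron use and duration by arm.

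Do not carry the last pre-iron value forward in the confirmatory test. Do not adjust for post-dose iron as a covariate, because it is itself affected by treatment.

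The cost is wording, one extra covariate and one extra analysis. No new data are needed, since iron intake is already assessed at the visits and concomitant medication is recorded.
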